
Sponsor: Ampio Pharmaceuticals, Inc.	Investigational Product: Ampion™	Developmental Phase: Phase 3
Test Product, Dose and Mode of Administration: Ampion, 4 mL, single intra-articular injection in the knee		
Reference Therapy, Dose and Mode of Administration: Saline, 4 mL, single intra-articular injection in the knee		
Study Duration: 24 weeks		
Criteria for Evaluation: Safety: Adverse events, physical examination, and vitals Efficacy: WOMAC osteoarthritis Index 3.1 and PGA		
Statistical Methods: The co-primary efficacy endpoints are the change from Baseline to Week 12 in the WOMAC A pain score and the WOMAC C function score. The primary efficacy analysis will use the intent-to-treat (ITT) analysis population with the per-protocol (PP) analysis population as supportive. WOMAC A pain and WOMAC C function scores will be analyzed using mixed-effects models with repeated measures (MMRM) with treatment assignment, week, and baseline WOMAC A pain scores and WOMAC C function scores, respectively, as covariates, with comparisons between Ampion and saline. All treatment emergent adverse events (TEAEs) will be reported by randomization assignment. There will be no statistical tests for incidence and severity of TEAEs.		

TABLE OF CONTENTS

PROTOCOL SYNOPSIS	3
LIST OF ABBREVIATIONS AND DEFINITION OF TERMS.....	11
1 INTRODUCTION.....	13
1.1 Study Drug.....	14
1.2 Background to the Disease	14
1.3 Previous Human Experience	15
1.4 Preclinical Data	15
1.4.1 Pharmacology Studies	15
1.4.2 Toxicity and Safety Studies.....	16
1.5 Clinical Experience	16
2 RATIONALE FOR THE STUDY	19
2.1 Rationale for the Doses and the Dosing Regimen.....	19
3 STUDY DESIGN	20
3.1 Study Design Overview.....	20
3.2 Study Objectives.....	21
3.2.1 Primary Objective.....	21
3.2.2 Secondary Objectives	21
3.2.3 Exploratory Objectives	21
3.3 Safety Monitoring Committee.....	21
3.4 Stopping Rules.....	22
3.5 Study Endpoints.....	22
3.5.1 Co-Primary Endpoint.....	22
3.5.2 Secondary Endpoints	22
3.5.3 Exploratory Endpoints.....	22
3.6 Blinding and Randomization.....	23
3.7 Code-breaking	23
4 SELECTION OF PATIENTS	24
4.1 Number of Patients	24
4.2 Recruitment Methods	24
4.3 Inclusion Criteria	25
4.4 Exclusion Criteria	25
4.5 Inclusion of Patients Incapable of Giving Informed Consent	26
5 STUDY PLAN AND PROCEDURES	27
5.1 Description of Study Visits	27
5.1.1 Visit -1 (Day -28 through Day 0, in-clinic): Screening.....	27

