10.3.4 Statistical Analysis of Co-Primary Effectiveness Endpoints

A mixed-effects model with repeated measures (MMRM) will be used to test the main effect of change in WOMAC A weekly pain score (determined as the average of Daily Pain measurements taken at Baseline and Week 12) from Baseline of Ampion vs. saline at 12 weeks. The model will include change from Baseline measures at 2, 4, 6, 8, 10, and 12 weeks. Treatment assignment, week, and Baseline WOMAC A measure will be included as fixed effects. Patient ID will be included to capture repeated measures using a compound symmetric covariance matrix for residuals. The primary hypothesis test for pain is the change in pain at 12-weeks at the one-sided $\alpha = 0.025$ level.

The same model will be used to test the effect of WOMAC C function change from Baseline of Ampion vs. saline at 12 weeks. WOMAC C will be tested at one sided $\alpha = 0.025$. Because both endpoints have to achieve statistical significance, this pairing ensures the one-sided Type I error control at the 0.025 level.

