10.3.11.4 Safety data

Safety data will be evaluated by changes in vital sign measurements and the frequency and severity of AEs. Concomitant medication will be recorded for safety.

Adverse events:

The Investigator is responsible for monitoring the safety of patients who have enrolled in the study. All AEs considered to be possibly related to Ampion will be followed until the event resolves or stabilized without further change. Patients will be followed for the occurrence of AEs until 12 weeks after the first dose of study medication.

Investigators are required to document all AEs occurring during the clinical trial, commencing with the first day of treatment and including the protocol-defined post-treatment follow-up period on the appropriate CRF pages.

The severity of AEs (mild, moderate, severe), relatedness (related, possibly related, unrelated) along with the duration, action taken, and outcome (e.g., study withdrawal) will also be recorded. In addition, events meeting the criteria of a SAE) must be reported to the Sponsor within 24 hours on the SAE reporting forms.

10.3.11.5 Efficacy data:

All efficacy variables will be assessed at Baseline (Day 0), Week 2 (Day 14 ± 7), Week 4 (Day 30 ± 7), Week 6 (Day 42 ± 7), Week 8 (Day 56 ± 7), Week 10 (Day 70 ± 7) and Week 12 (Day 84 ± 7). For analysis of baseline WOMAC A pain, the baseline pain score is the average of all scores measured during days -7 to 0, prior to injection of treatment. For analysis of week 12 WOMAC A pain, the week 12 pain score is the average of all scores measured during the seven days prior to and including the Week 12 office visit.

All statistical tests will be two-sided, except the co-primary endpoints which require superiority in pain vs. saline control in pain and superiority to baseline in function.

Unless otherwise specified, continuous variables will be summarized with the number of non-missing observations, mean, standard deviation, median, minimum, and maximum displayed. Categorical data will be summarized as counts and percentages. All efficacy assessments will be summarized as the measured value and as the change from Baseline by treatment at each timepoint. Summary statistics will include number of observations, mean, standard deviation, median, minimum and maximum. Change from Baseline will also include a 95% confidence interval.

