10.4.3 Exploratory Endpoints

- Change in WOMAC B stiffness sub score between Baseline and Weeks 2, 4, 6, 8, 10, 12 and 24
- Response status based on the OMERACT-OARSI criteria at Weeks 2, 4, 6, 8, 10, 12 and 24
- Proportion of treatment failures at Week 12
- Change in pain and function CDF plot for Ampion and saline patients
- A Bayesian meta-analysis for LK WOMAC A pain sub score including KL 4 patients from studies AP-003-A, AP-003-B, AP-003-C, AP-004, and AP-013
- Change in WOMAC A pain sub score between Baseline and Weeks 2, 4, 6, 8, 10, and 24
- Change in PGA between Baseline and Weeks 2, 4, 6, 8, 10, and 24
- Change in WOMAC C physical function sub score between Baseline and Weeks 2, 4, 6, 8, 10, and 24
- If collected, difference in urine analysis between treatment groups at Week 12

The Bayesian meta-analysis methodology is described in the Statistical Analysis Plan.

Percent responders using the OMERACT-OARSI criteria will be analyzed using separate logistic regression models for each visit.

Proportion of treatment failures will be analyzed using Fisher's exact tests.

Analysis with exploratory biomarkers, such as those for analgesic use and chemokines and cytokines associated with inflammation and cartilage regeneration may be analyzed to compare differences between treatment groups using urine samples collected at Week 12.

All other exploratory endpoints will be analyzed as the difference between treatment groups at each time point extracted from the MMRM model, adjusted for Baseline value.

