### **3. STUDY ENDPOINTS AND COVARIATES**

#### **3.1 Primary Endpoints**

The trial will test whether Ampion can produce a superior improvement in pain vs. saline control and a superior improvement in function vs. saline. This goal is achieved using two co-primary endpoints:

Change in the WOMAC A weekly pain sub score between Baseline and Week 12  
Change in WOMAC C physical function sub score between Baseline and Week 12

An average of the daily WOMAC A pain assessments will be used to calculate the weekly pain score, at baseline and at Week 12.

Mean 12-week change in the WOMAC A pain score will be compared between Ampion and saline control. Mean 12-week change in WOMAC C physical function score will be compared between Ampion and saline control.

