### **3.4 Covariates**

Analyses of change will include treatment assignment, Week, and the Baseline measure of the variable being analyzed as a covariate in the model.

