### 8.6.1 Primary Effectiveness Endpoints

Change in WOMAC A pain score as measured by a 5-point Likert scale, from Baseline to Week 12, will be analyzed by including change from Baseline at 2, 4, 6, 8, 10, and 12 weeks in a mixed-effects model with repeated measures (MMRM). Treatment assignment Week, the treatment\*week interaction and Baseline WOMAC pain score will be included as fixed effects. Patient ID will be included to denote repeated measures and a compound symmetric covariance matrix will be used for residuals. Least squares means and treatment difference with 95% confidence intervals will be presented.

SAS code used will follow the following format:

```
Proc mixed;
  Class PtID treatment week;
  Model delta_pain = treatment baseline_pain week treatment*week;
  Repeated week / subject=newID type = CS;
  Lsmeans active*week / SLICE=week diff;
run;
```

The primary analysis will include the repeated measures of WOMAC C function sub score from Baseline to Weeks 2, 4, 6, 8, 10, and 12 and will use a mixed-effects model with repeated measures MMRM model, with Week as a fixed effect, and including patient ID as a repeated measure with a compound symmetric covariance matrix for residuals.

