The primary effectiveness endpoints will be analyzed using the ITT analysis population. In order to preserve the randomization, any missing values at 12 weeks will be imputed. Week 12 visit data collected more than 14 days after the target day of 84 will be used and not imputed. The primary method of imputation will be the full conditional specification method with predictive means matching (Berglund & Heeringa 2014). This imputation method uses all observed values of the primary outcome at Baseline, 2, 4, 6, 8, 10, and 12 weeks to impute an individual's missing values. To determine the possible effect of missing data on the primary analysis, the following sensitivity analyses will be performed: 1 – multiple imputation (SAS PROC MI, using the default method MCMC along with PROC MIANALYZE); 2 – last observation carried forward (LOCF) 3 – a regression-based prediction using individual's prior data and time of prior data will be used to impute Week 12 data; and 4 – a conservative imputation approach will be performed where the greatest pain reduction observed in the study will be imputed for the saline arm and the worst change in pain score observed in the study will be used to impute missing 12-week values in the Ampion arm. Any imputed value that results in more than one decimal place will be rounded to one decimal place.

An analysis of site effect will be performed. If the main effect has a p-value of 0.15 or smaller in a secondary analysis, site will be included in the model and summaries of the primary effectiveness endpoint will be produced by site as well as pooled over sites.

WOMAC A Pain scores and the WOMAC C functions scores and their respective change and percent change from Baseline will be summarized by visit. The Change from Baseline scores will include a 95% CI. For the WOMAC A Pain subscore and WOMAC C Function subscore, a test for the main effect for Ampion vs. saline will be included on the summary tables at weeks indicated as primary or secondary endpoints.

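### The co-primary WOMAC C model is specified in conflicting ways: one version has no treatment term, and the versions with one omit treatment-by-week, so none gives the Week 12 difference that the trial is meant to test

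*SAP*

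**What the plan says.** The endpoint is clear. SAP 3.1 defines it as the change from Baseline to Week 12 and says: "Mean 12-week change in WOMAC C physical function score will be compared between Ampion and saline control". Protocol 10.3.4 also places the test at 12 weeks, and the hypotheses (Protocol 10.3.5, SAP 4.1) compare Ampion with saline.

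The model is not clear:

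- **Protocol 10.4.1 and SAP 8.6.1**, the sections that define the co-primary analyses, give the WOMAC C model "with Week as a fixed effect, and including patient ID as a repeated measure with a compound symmetric covariance matrix for residuals". No other fixed effect is named.
- **Protocol Synopsis, Statistical Methods**, describes models for both scores "with treatment assignment, week, and baseline WOMAC A pain scores and WOMAC C function scores, respectively, as covariates".
- **Protocol 10.3.4** says of pain: "Treatment assignment, week, and Baseline WOMAC A measure will be included as fixed effects". It then applies the same model to WOMAC C.
- **SAP 3.4** says: "Analyses of change will include treatment assignment, Week, and the Baseline measure of the variable being analyzed as a covariate in the model".
- **SAP 8.6.1, pain paragraph and SAS code**, is the only primary model with a treatment-by-week term. The code is written for pain, and the WOMAC C paragraph after it does not refer back to it.
- **SAP 8.6.1, summary tables**: "a test for the main effect for Ampion vs. saline will be included on the summary tables".
- **Protocol 10.3.11.5** describes the co-primary tests as requiring "superiority in pain vs. saline control in pain and superiority to baseline in function".
- **Protocol 10.4.3**: "All other exploratory endpoints will be analyzed as the difference between treatment groups at each time point extracted from the MMRM model".

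**The concern.** There are two separate faults.

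First, a model whose only fixed effect is Week has no parameter for Ampion against saline, so it cannot test the co-primary function hypothesis. Protocol 10.3.11.5 adds to the confusion by describing a comparison with baseline, which is a different hypothesis.

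Second, the passages that put treatment back do not reach the stated target. With treatment, week and baseline as the only terms, the model forces the treatment difference to be the same at every visit. The quantity tested is an average over Weeks 2 to 12. The per-visit differences promised in Protocol 10.4.3 would all be the same number.

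Both co-primary endpoints must succeed for the trial to succeed. WOMAC C sets the sample size (Protocol 4.1, SAP 2.4), and the promising-zone decision rests on it alone (Protocol 3.3 and 10.3.9, SAP 7). Neither interim section says which estimate enters the conditional power. Two competent programmers could follow the text and reach different final results or different interim decisions. A choice made after unblinding would be open to the charge that the data guided it.

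**Working it through.** **1. The terms listed for WOMAC C**

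| Place | Treatment | Week | Baseline | Treatment-by-week |
|---|---|---|---|---|
| Protocol 10.4.1 | no | yes | no | no |
| SAP 8.6.1 | no | yes | no | no |
| Protocol Synopsis | yes | yes | yes | no |
| Protocol 10.3.4 | yes | yes | yes | no |
| SAP 3.4 | yes | yes | yes | no |

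**2. What the model without interaction estimates**

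Under compound symmetry with complete or fully imputed visits, the treatment coefficient is the simple mean of the six visit differences. This was confirmed on one simulated data set with 200 per arm, correlation 0.5 and an effect falling to zero at Week 12. The coefficient without interaction was -0.0455. The mean of the six visit differences from the interaction model was also -0.0455, while its Week 12 difference was +0.0417. With missing visits the coefficient becomes a weighted mean.

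**3. The plan's own figures**

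Pain: difference 0.83 - 0.62 = 0.21, SD 0.85, one-sided 0.025, 90% power.

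- n per arm = 2 × (1.960 + 1.2816)² × (0.85/0.21)², which rounds up to 345. The total is 690, as stated.
- Power is 97.8% at 1,034 patients and 97.2% at 984, in line with the stated 97%.

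The function effect and SD are not given, so 984 cannot be rebuilt directly. Solving back, the implied effect is d = (1.960 + 1.2816) × √(2/492) = 0.2067 SD.

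**4. Power at the final analysis, 492 per arm**

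The between-visit correlation ρ and the shape of the effect over time are assumptions; the documents give neither.

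- SE of the Week 12 contrast (SD units) = √(2/492).
- SE of the six-visit average = √(2/492) × √((1 + 5ρ)/6). The second factor is 0.764 at ρ = 0.5 and 0.866 at ρ = 0.7.
- Power = Φ(share × d / SE - 1.96), where share is the effect tested as a fraction of d.

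| Effect over time | Average share of d | Averaged test, ρ = 0.5 / 0.7 | Week 12 contrast |
|---|---|---|---|
| Constant | 1 | 0.989 / 0.963 | 0.90 |
| Straight line from zero at baseline to d at Week 12 | (2+4+6+8+10+12)/(6×12) = 0.583 | 0.697 / 0.588 | 0.90 |
| d at Weeks 2-10, zero at Week 12 (extreme) | 5/6 | 0.943 / 0.877 | 0.025 |

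Simulation of 4,000 trials per case gave 0.989/0.961, 0.695/0.588 and 0.940/0.876. In a milder waning case, with d at Week 2 falling linearly to zero at Week 12 (share 0.5), the averaged test rejects 71% to 47% of the time for ρ from 0.3 to 0.7, against 2.5% for the Week 12 contrast.

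**5. Interim, 362 per arm, planned final 1,034**

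Conditional power at the expected z is CP = 1 - Φ[(1.96√1034 - z√724)/√310 - z√310/√724].

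Rising case:

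- Week 12 contrast: z = 0.2067/√(2/362) = 2.78, CP = 0.994. No increase.
- Averaged estimate: z = 0.583 × 2.78/0.764 = 2.12 at ρ = 0.5 and 0.583 × 2.78/0.866 = 1.87 at ρ = 0.7. CP = 0.854 and 0.694. Both lie between 0.391 and 0.90, so the sample size would be increased.
- At ρ = 0.3 the factor is 0.645, z = 2.51 and CP = 0.97. No increase.

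Linear waning case:

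- Week 12 contrast: z = 0, CP = 0.0002. No increase.
- Averaged estimate: z = 0.5 × 2.78 divided by 0.645, 0.764 and 0.866, giving 2.15, 1.82 and 1.61 for ρ = 0.3, 0.5 and 0.7. CP = 0.87, 0.65 and 0.47. All fall in the promising zone.

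**The case against.** The strongest reply is that the intent is plain. Many passages require a saline comparison for function, and a model with no treatment term would fail visibly and could not give a wrong answer unnoticed. That is fair, so the missing treatment term is mainly a drafting error. It is still the wording in both sections that define the analysis.

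On the interaction, several passages suggest that it was meant. The summary-table sentence in SAP 8.6.1 goes on to tie the test to the visits named as primary or secondary endpoints. SAP 8.6.5 analyses WOMAC C at separate weeks with the primary-analysis model. Protocol 10.4.3 extracts differences by time point. SAP 3.4 is a general covariate list that also covers pain, where SAP 8.6.1 adds the interaction. This stands as evidence of intent, but none of it specifies the co-primary WOMAC C test. SAP 8.6.5 points to a section that holds two different models, and the summary-table sentence still calls the test a main effect.

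The interim illustration depends on its scenario, and this also stands. With a constant effect, both estimates give a conditional power above 0.99 and no increase. With the effect gone only at Week 12, the conditional powers are 0.0002 and 0.988-0.999, but both lead to 1,034 patients. If the effect rises from half to full size, the averaged value is 0.95 or more and nothing changes. In the straight-line rise the decision changes at ρ of 0.5 and 0.7 but not at 0.3. The figures show that the readings can diverge; they do not predict this trial.

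**Conclusion.** The concern holds. As written, the co-primary function analysis is either a model with no treatment comparison or a model of an averaged effect. No passage specifies a WOMAC C model that yields the Week 12 difference named as the endpoint. This conclusion rests on the text and on a property of the model, and it needs no assumption about correlation or trajectory beyond an effect that may vary over visits.

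The size does depend on assumptions: 0.207 SD implied by the plan's 984 patients, complete or imputed data at six visits, exchangeable correlation, and the chosen trajectories. Within them, the averaged test ranges from a gain of 6 to 9 percentage points of power (constant effect) to a loss of 20 to 31 points (linear rise). It can also declare success in most trials where nothing remains at Week 12. The same interim data can fall in different promising-zone categories. Because this endpoint must succeed and governs the sample size, the plan should be corrected before any unblinded look.

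**What to change.** - **Protocol 10.4.1 and SAP 8.6.1:** write the WOMAC C model as change = treatment + week + treatment-by-week + baseline WOMAC C. Name the Ampion-minus-saline contrast at Week 12, one-sided 0.025, as the test.
- **SAP 8.6.1 code:** give WOMAC C its own block. The existing pain code calls `active` and `newID`, which its Class statement does not declare (it declares `treatment` and `PtID`). Make the names match.
- **Protocol Synopsis, 10.3.4, the pain model in 10.4.1, and SAP 3.4:** add treatment-by-week for the co-primary models, so that the protocol agrees with the SAP pain model.
- **SAP 8.6.1, summary tables:** replace the main-effect test with the week-specific contrast.
- **Protocol 10.3.11.5:** change the function comparison from baseline to saline.
- **Protocol 10.3.9 and SAP 7:** state that conditional power uses this same Week 12 contrast.

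A separate minor point: the Week 10 cells for WOMAC B/C and PGA appear blank in Protocol Table 6.1 and SAP 13, although Protocol 5.1.9, 6.1.1, 6.1.2 and the model use Week 10. Check the source tables and reconcile them. The main finding does not depend on this.

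The cost is protocol and SAP wording plus one block of code, before the interim unblinding. No new data are needed.

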### 8.6.2 Secondary Effectiveness Endpoints

Secondary effectiveness endpoints will be analyzed using the ITT and the PP analysis populations. All secondary efficacy tests will be performed and reported with one-sided p-values for superiority of Ampion.

Change from Baseline to 2, 4, 6, 8, 10, 12, and 24 weeks for the PGA will be analyzed using a MMRM model. Treatment assignment, Week, and Baseline PGA will be included as fixed effects and a compound symmetric covariance matrix for residuals to reflect the repeated measures.

Change from Baseline to 12 weeks for the 100mm VAS Pain Score will be analyzed using a MMRM model. Treatment assignment, and Baseline PGA will be included as fixed effects and a compound symmetric covariance matrix for residuals to reflect the repeated measures.

Use of rescue analgesia (amount of acetaminophen used) will be compared by treatment arm. A Wilcoxon rank-sum test will be used to compare overall pill count use over the study between saline and Ampion.

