10.4.2 Secondary Endpoints

- Change in PGA between Baseline and Week 12
- Change in the 100 mm VAS Pain Scale between Baseline and Week 12
- Use of rescue analgesia (amount of acetaminophen used between Baseline and Week 12)
- Incidence and severity of treatment-emergent adverse events (TEAEs)

A serial gatekeeping approach will be used to test the secondary endpoints in a sequential manner (i.e. PGA, 100 mm VAS, rescue analgesia).

The difference between treatment groups in the mean change in PGA from Baseline to Week 12 will be analyzed using a similar MMRM model, with Treatment assignment, Week, and Baseline value as fixed effects and including patient as a repeated measure with a compound symmetric covariance matrix for residuals.

The difference between treatment groups in the mean change in 100 mm VAS from Baseline to Week 12 will be analyzed using a similar MMRM model, with Treatment assignment, and Baseline value as fixed effects and including patient as a repeated measure with a compound symmetric covariance matrix for residuals.

The difference between treatment groups in the amount of acetaminophen used between Baseline and Week 12 will be analyzed with a Wilcoxon rank-sum test.

All secondary efficacy analyses will be reported with one sided p-values and successively compared to a critical level of 0.025 if each preceding test was significant.

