#### **3.2 Secondary Endpoints**

- Change in PGA between Baseline and Week 12
- Change in 100mm VAS Pain scale between Baseline and Week 12
- Use of rescue analgesia (amount of acetaminophen used between Baseline and Week 12)
- Incidence and severity of treatment-emergent adverse events (TEAEs)

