### 8.6.5 Exploratory Endpoints

A Bayesian meta-analysis for Likert WOMAC A pain subscore including KL4 patients from studies AP-003-A, AP-003-B, AP-003-C, AP-004, and AP-013. The model is constructed for WOMAC A change from baseline for patient  $i$  in study  $j$

$$Y_{i,j} \sim N(\mu_{i,j}, \sigma^2)$$

$$\mu_{i,j} = \alpha_j + \delta_j T_i + \beta BL_i$$

$$\alpha_j \sim N(\alpha, \sigma_\alpha^2)$$

$$\delta_j \sim N(\delta, \sigma_\delta^2)$$

$$\alpha \sim N(0, 100)$$

$$\delta \sim N(0, 100)$$

$$\sigma_\alpha \sim U(0, 10)$$

$$\sigma_\delta \sim U(0, 10)$$

$$\sigma \sim U(0, 10)$$

Where  $T_i$  is the treatment assignment (0 saline or control; 1=Ampion) and  $BL_i$  is the baseline WOMAC A score.  $\alpha_j$ 's represent the control means across studies.  $\delta_j$ 's represent the treatment effects across studies.  $\sigma_\alpha$  and  $\sigma_\delta$  represent the heterogeneity of control rates and treatment effects, respectively. Sensitivity analyses will be reported that increase the priors on the variance parameters from  $U(0, 10)$  to  $U(0, 500)$ . The posterior means and 95% credible intervals will be reported for each treatment by study and treatment effect by study.

Change in WOMAC A pain sub score between Baseline and Weeks 2, 4, 6, 8, 10, and 24 will be analyzed using the MMRM model described for the primary analysis.

Change in WOMAC B stiffness sub score between Baseline and Weeks 2, 4, 6, 8, 10, 12 and 24 will be analyzed using the MMRM model described for the primary analysis.

Change in WOMAC C physical function sub score between Baseline and Weeks 2, 4, 6, 8, 10, and 24 will be analyzed using the MMRM model described for the primary analysis.

Change in PGA between Baseline and Weeks 2, 4, 6, 8, 10, and 24 will be analyzed using the MMRM model described for the primary analysis.

OMERACT-OARSI responder status, defined using Scenario D criteria, will be analyzed using separate logistic regression models for each visit.

Treatment failures will be analyzed with a Fisher's exact test.

Cumulative distribution function (CDF) plots will be used to compare WOMAC A pain and WOMAC C function endpoints for Ampion vs. saline arms.

If collected, the differences in urine analysis will be evaluated between treatment groups at Week 12.

Continuous secondary endpoints and their change from Baseline will be summarized by visit and treatment arm. Change from Baseline will include a 95% CI.

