### **8.6.7 Multiplicity Adjustment**

Hierarchical testing for the ITT analysis population will be applied to the analysis of the primary endpoints. It will also be utilized for the secondary endpoints, assuming significance of the co-primary effectiveness endpoints are established. Given significance

for the primary effectiveness tests (WOMAC A and WOMAC C (as specified)), then and only then would PGA score be tested at the one-sided alpha of 0.025; if the PGA score is significant then and only then, will the 100 mm VAS hypotheses be tested at a one-sided alpha of 0.025; if the 100 mm VAS hypothesis is significant then, and only then, will the amount of rescue analgesia through Week 12 be tested at a one-sided alpha 0.025. Multiplicity adjustment will not be applied to exploratory endpoints.

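### The first secondary test (PGA) is named for Week 12, but its model tests the average over all visits to Week 24; the VAS covariate and rescue period also conflict

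*SAP*

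**What the plan says.** **PGA.** SAP 3.2 defines the endpoint as "Change in PGA between Baseline and Week 12". SAP 8.6.2 gives the analysis: "Change from Baseline to 2, 4, 6, 8, 10, 12, and 24 weeks for the PGA will be analyzed using a MMRM model". The terms follow: "Treatment assignment, Week, and Baseline PGA will be included as fixed effects", with a compound-symmetric residual matrix. SAP 8.6.7 places PGA directly after the co-primaries ("then and only then would PGA score be tested at the one-sided alpha of 0.025") and names no week. Protocol 10.4.2 does name Week 12, but its model also lacks an interaction: "with Treatment assignment, Week, and Baseline value as fixed effects and including patient as a repeated measure".

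Two other places in the SAP differ. The WOMAC A code in 8.6.1 reads "Model delta_pain = treatment baseline_pain week treatment*week" and compares arms within week. For the exploratory weeks, SAP 8.6.5 says "Change in PGA between Baseline and Weeks 2, 4, 6, 8, 10, and 24 will be analyzed using the MMRM model" of the primary analysis; that list leaves out Week 12.

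**VAS.** SAP 8.6.2 states that "Treatment assignment, and Baseline PGA will be included as fixed effects". SAP 3.4 and protocol 10.4.2 call for the baseline of the variable being analysed.

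**Rescue.** SAP 8.6.2 compares tablet counts over the whole study, which SAP 5.2 ends at Week 24. SAP 3.2, SAP 8.6.7 and protocol 10.4.2 stop at Week 12.

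**The concern.** A model without a treatment-by-week term has one treatment effect, common to all visits. Its Week 12 least-squares mean difference is that same common coefficient, so asking for a Week 12 contrast would not by itself give a Week 12 test. Going back to the protocol does not help, because 10.4.2 omits the interaction too; the SAP then adds Week 24. The exploratory PGA weeks, on the other hand, go to a model whose WOMAC A form has the interaction, so the same PGA data get two different models.

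PGA decides whether VAS and rescue may be tested at all. A pass could be reported as a Week 12 benefit when it came from earlier visits. A real Week 12 benefit could also be diluted and end the sequence. For rescue, two periods are written into the SAP, so the tested period could be chosen after the data are seen.

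**Working it through.** **Figures in the plan.** None is given for PGA, VAS or rescue. The pain figures do reproduce (difference 0.21, SD 0.85, one-sided 0.025): 2 × (1.960 + 1.282)² × (0.85/0.21)² = 344.3, so 345 per arm, or 690 in total as stated. Power at 517 per arm is 97.8%, against the stated 97%.

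**Visit weights.** Let d be the vector of k between-arm differences in mean change, one per visit. With complete data and n per arm, its covariance is (2/n)V in units of the single-visit residual variance, where V has 1 on the diagonal and ρ elsewhere. Week effects absorb the visit means, so the treatment estimate is (1′V⁻¹d)/(1′V⁻¹1). Under compound symmetry V⁻¹1 is proportional to 1. Hence:

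- estimate = simple mean of the k differences, so each visit has weight 1/k whatever ρ is;
- variance = (2/n) × (1 + (k−1)ρ)/k.

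SAP 8.6.2 lists k = 7 visits, giving a weight of 1/7 = 0.143. Both schedule tables show no PGA at Week 10, although protocol 5.1.9 includes it; without it k = 6 and the weight is 1/6 = 0.167. Solving the weighted least-squares equations numerically gave these weights at ρ = 0.3, 0.5 and 0.7.

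**What this can do to the test.** The effect profiles and ρ are assumptions, because the documents give none for PGA. Effects are in SD units at Weeks 2, 4, 6, 8, 10, 12, 24, with n = 517 per arm and one-sided 0.025. PGA is taken as independent of the co-primaries, given that both succeeded.

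- *Fade:* 0.20, 0.20, 0.20, 0.15, 0.10, 0, 0. Mean 0.85/7 = 0.121, or 0.75/6 = 0.125 without Week 10.
- *Build:* 0.05, 0.08, 0.12, 0.15, 0.18, 0.2067, 0.10. Mean 0.127 or 0.118. The 0.2067 is the standardized effect implied by 984 patients at 90% power: 3.2415 × √(2/492).
- *Constant:* 0.20 throughout.

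Example (fade, k = 7, ρ = 0.5): SE = √(2/517 × 4/7) = 0.0470; z = 0.1214/0.0470 = 2.58; P(reject) = Φ(2.58 − 1.96) = 73%. For a Week 12 test SE = √(2/517) = 0.0622; under build, z = 0.2067/0.0622 = 3.32 and power is 91%.

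| Profile | 7 visits, ρ 0.5 / 0.6 | 6 visits, ρ 0.5 / 0.6 | Week 12 test |
|---|---|---|---|
| Fade | 73.3% / 67.3% | 74.9% / 69.2% | 2.5% |
| Build | 76.9% / 71.0% | 69.8% / 64.0% | 91.4% |
| Constant | 98.9% / 97.8% | 98.8% / 97.6% | 89.5% |

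**VAS.** Relative SE from using the wrong baseline = √[(1 − r²_PGA)/(1 − r²_VAS)], where each r is the correlation of that baseline with VAS change. With r_VAS 0.4 to 0.5 and r_PGA 0 to 0.2 (assumed), the ratio runs from √(0.96/0.84) = 1.07 to √(1/0.75) = 1.15.

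**Rescue.** Week 12 is Day 84 and Week 24 nominally Day 168, so 84 of 168 days fall after the endpoint. With the Day 174 printed in the schedules it is 90 of 174. Either way it is about half. No effect on the test was estimated.

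**The case against.** The intent is fairly clear. Week 12 is named as the PGA endpoint in the SAP and in the protocol. The protocol lists its WOMAC A terms in the same shorthand, and the SAP then supplies the interaction for pain. Protocol 10.4.3 takes the remaining exploratory endpoints at each time point from the model. An analyst might well build by-visit PGA contrasts anyway. That argues for an incomplete specification rather than a deliberate choice of an average. It does not supply the missing term, since the terms are listed explicitly and no section gives a by-week PGA estimate at Week 12.

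The rejection rates depend on chosen profiles and a narrow ρ. Over ρ 0.3 to 0.7, fade runs from 62 to 88%; build runs from 66 to 90% with seven visits and 59 to 84% with six. If the build effect is held at 0.207 to Week 24, seven-visit power is 75 to 95% and can exceed the Week 12 test. The fade case also needs PGA to have no Week 12 effect after pain and function both succeeded, which is unlikely for related self-reports from the same patients. If pain also had no Week 12 effect, PGA would be reached at most 2.5% of the time. These points stand. They limit the illustrations and leave the weights unchanged.

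The VAS covariate is probably a copying slip, and the rescue wording in 8.6.2 is outnumbered by the other sections. Both still need correcting.

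**Conclusion.** As written, the PGA test does not match its endpoint. Week 12 carries 1/7 of the weight (1/6 without a Week 10 PGA), and the test estimates an average to Week 24. The weights are exact for complete data. SAP 7.2 imputes missing PGA in the ITT set, so they are a close guide. With unimputed gaps the weights shift, but the test remains a cross-visit average. The table of rejection rates is illustrative, and the mismatch can raise or lower the chance of a pass.

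The VAS comparison stays unbiased and loses only precision (SE 7 to 15% wider under the assumed correlations). The rescue period is an internal contradiction of unknown effect.

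All of this matters only once both co-primaries have succeeded, and the co-primary tests are untouched. It should be corrected before unblinding.

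**What to change.** In SAP 8.6.2:

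1. **PGA:** use the WOMAC A model form (treatment, baseline PGA, week, treatment-by-week) and name the Week 12 treatment difference as the test in the sequence, here and in 8.6.7. Keep all other weeks, including Week 24, exploratory, and say whether Week 24 data enter the fitted model. Record in SAP section 9 that this adds an interaction missing from protocol 10.4.2. Reconcile the Week 10 PGA entry between the schedules and the visit text.
2. **VAS:** replace baseline PGA with baseline VAS, and state that the Week 12 value is the weekly average of the daily scores. With one value per patient the model reduces to ANCOVA.
3. **Rescue:** replace the whole-study period with Baseline to Week 12.

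The cost is SAP wording only. The analyses use data the plan already collects, and no change to sample size or alpha is needed.
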